10.1 EXPOSURE TO STUDY DRUG

Descriptive statistics will be provided for the total (cumulative) doses taken and total duration of treatment by treatment group for each study part. The total duration of treatment is calculated as (treatment stop date – treatment start date) + 1. If treatment stop date is missing, the date of final clinic visit will be used. By subject listing of study drug exposure will also be presented by study part and treatment group for each treatment cycle and all cycles combined.

10.2 ADVERSE EVENTS

An adverse event is defined as any untoward medical occurrence in a patient administered a medicinal product that does not necessarily have a causal relationship with this treatment. This includes an exacerbation of pre-existing conditions or events, inter-current illnesses, drug interaction, or the significant worsening of the indication under investigation that is not recorded elsewhere in the eCRF under specific efficacy assessments. The reporting period of an AE begins from the time that the patient provides informed consent through and including 30 calendar days after the last administration of BVD-523 (or at the time when a patient begins a new anti-cancer therapy). Anticipated fluctuations of pre-existing conditions, including the disease under study that does not represent a clinically significant exacerbation or worsening, need not be considered AEs.

The severity of an AE will be graded according to the National Cancer Institute (NCI) Common Terminology Criteria for Adverse Events (CTCAE), version 4 with values of Grade 1 to Grade 5 (increased in severity). For AEs not covered by NCI CTCAE, the severity will be characterized as “mild,” “moderate,” or “severe” according to the following definitions:

- Mild (equivalent to Grade 1) events are usually transient and do not interfere with the patient’s daily activities.
- Moderate (equivalent to Grade 2) events introduce a low level of inconvenience or concern to the patient and may interfere with daily activities.
- Severe (equivalent to Grade 3) events interrupt the patient’s usual daily activities.

All AE relationship to the study drug, BVD-523, are classified as “unrelated,” “possibly related,” or “related.”

AE Coding

Any AE including SAE in verbatim term will be coded in accordance with the Medical Dictionary for Regulatory Activities (MedDRA®) dictionary version 16.0 to a system organ class (SOC) and preferred term (PT) within each SOC. Analysis of AEs will then be performed using SOCs and PTs.

Dose Limiting Toxicities, Maximum Tolerated Dose, and Recommended Phase 2 Dose

As specified in Section 2.1.1, a DLT for Part 2 is defined (per definition in protocol amendment 7) as a **BVD-523 related toxicity in the first 21 days** of treatment that results in:

- \geq Grade 4 hematologic toxicity for > 1 day;
- Grade 3 hematologic toxicity with complications e.g., thrombocytopenia with bleeding;
- \geq Grade 3 non-hematologic toxicity, except untreated nausea, vomiting, constipation, pain, and rash (these become DLTs if the AE persists despite adequate treatment), a doubling of AST/ALT in patients with grade 2 ALT/AST at baseline;
- A treatment interruption exceeding 5 days (or an interruption exceeding 7 days for rash, despite adequate treatment) in Cycle 1 (or inability to begin Cycle 2 for > 7 days) due to BVD-523-related toxicity³.

As specified in Section 2.1.1, the MTD is defined as the highest dose level at which $\leq 33\%$ of patients experience BVD-523 related DLTs in the first 21 days of treatment. The RP2D may be as high as the MTD and will be determined in discussion with the Clinical Investigators, the Medical Monitor, and the Sponsor. Observations related to pharmacokinetics (PK), pharmacodynamics (PD), and any cumulative toxicity observed after multiple cycles may be included in the rationale supporting the RP2D. Pharmacokinetic, pharmacodynamics, and/or Holter measurements may be suspended pending review of accumulated patient experience.

Treatment Emergent Adverse Event

A treatment emergent adverse event (TEAE) is any AE temporally associated with the use of BVD-523 (from BVD-523 initiation until 30 calendar days after the last administration of BVD-523), whether or not considered related to the study drug. If the onset of an AE is missing and the AE resolution date is either after the initial BVD-523 dose date or missing, then the AE will be considered treatment emergent.

AE Summaries

A subject who reported multiple AEs that map to a common PT or SOC is counted only once for that PT or SOC at the highest severity reported and at the greatest relationship to study drug.

The number and percentage of subjects who experienced at least one AE will be tabulated by SOC and PT with respect to dose level/treatment group for each study part. The same tabulation will also be applied to any SAE, any AE leading to premature discontinuation from the study, treatment emergent AEs and treatment-emergent SAEs.

³ For Amendments 1 and 2: A treatment interruption exceeding 3 days in Cycle 1 due to drug-related toxicity (or inability to begin Cycle 2 for > 7 days) due to drug-related toxicity.

For Amendment 3: A treatment interruption exceeding 5 days in Cycle 1 due to drug-related toxicity (or inability to begin Cycle 2 for > 7 days due to drug-related AE)

For Amendments 4, 5, and 6: A treatment interruption exceeding 5 days (or an interruption exceeding 7 days for rash, despite adequate treatment) in Cycle 1 (or inability to begin Cycle 2 for > 7 days) due to BVD-523-related toxicity.

The number and percentage of subjects who experienced at least one AE will also be tabulated by SOC and PT within each dose level/treatment group with respect to relationship to study drug (unrelated, possibly related, and related) and severity (Grade 1 to Grade 5). Subject listings will also be provided for all AEs, all SAEs, all AEs leading to early discontinuation from the study and all AEs leading to study drug interruptions and length of interruptions.

Bar graphs of AEs in CTCAE Term will be displayed in decreasing order of incidence from most common to least common. Each bar in the plot will represent an AE in CTCAE Term. Severity of AE (grades) will be embedded in each bar using the percentages of patients in each AE grade. These plots will be provided for all AE tables produced.

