### **9.4 INTENSITY OF ADVERSE EVENTS**

The severity of the AE will be graded according to the NCI CTCAE Grading Scale Version 4.03 (see the NCI CTCAE web page at <http://ctep.cancer.gov> for details). For AEs not covered by NCI CTCAE, the severity will be characterized as “mild”, “moderate”, or “severe” according to the following definitions:

- Mild events are usually transient and do not interfere with the patient’s daily activities.
- Moderate events introduce a low level of inconvenience or concern to the patient and may interfere with daily activities.
- Severe events interrupt the patient’s usual daily activities.

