2 STUDY OBJECTIVES, TREATMENTS, AND ENDPOINTS

2.1 STUDY OBJECTIVES

2.1.1 Primary Objectives

To define the safety and tolerability of BVD-523 in patients with advanced malignancies by determining the dose-limiting toxicities (DLT), the maximum tolerated dose (MTD), and the recommended Phase 2 Dose (RP2D).

A DLT is defined (per definition in protocol amendment 7)¹ as a **BVD-523 related toxicity in the first 21 days** of treatment that results in:

- \geq Grade 4 hematologic toxicity for > 1 day;
- Grade 3 hematologic toxicity with complications e.g., thrombocytopenia with bleeding;
- \geq Grade 3 non-hematologic toxicity, except untreated nausea, vomiting, constipation, pain, and rash (these become DLTs if the adverse event (AE) persists despite adequate treatment), a doubling of AST/ALT in patients with grade 2 ALT/AST at baseline;
- A treatment interruption exceeding 5 days (or an interruption exceeding 7 days for rash, despite adequate treatment) in Cycle 1 (or inability to begin Cycle 2 for > 7 days) due to BVD-523-related toxicity.

¹ The original protocol, as well as amendments 1, 2, 3, and 4 defined DLTs slightly differently. In these amendments, a DLT was defined as above except for the following:

- \geq Grade 3 non-hematologic toxicity, except untreated nausea, vomiting, constipation, pain, and rash (these become DLTs if the adverse event (AE) persists despite adequate treatment)
- “A doubling of AST/ALT in patients with grade 2 ALT/AST at baseline” was introduced in Amendment 5

Treatment interruption DLTs were also defined slightly differently in different protocols:

- For the original protocol and Amendments 1 & 2: A treatment interruption exceeding 3 days in Cycle 1 due to drug-related toxicity (or inability to begin Cycle 2 for > 7 days) due to drug-related toxicity.
- For Amendment 3: A treatment interruption exceeding 5 days in Cycle 1 due to drug-related toxicity (or inability to begin Cycle 2 for > 7 days due to drug-related AE)
- For Amendment 4, 5, 6 & 7: A treatment interruption exceeding 5 days (or an interruption exceeding 7 days for rash, despite adequate treatment) in Cycle 1 (or inability to begin Cycle 2 for > 7 days) due to BVD-523-related toxicity.

The MTD is defined as the highest dose cohort at which $\leq 33\%$ of patients experience BVD-523 related DLTs in the first 21 days of treatment.

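### The SAP's severity conversion for adverse events outside CTCAE stops at Grade 3, so a fatal or life-threatening one would be tabulated as Grade 3

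*SAP*

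**What the plan says.** - **Main scale, SAP 10.2.** Severity follows CTCAE "version 4 with values of Grade 1 to Grade 5 (increased in severity".
- **Fallback scale, SAP 10.2.** Events outside CTCAE get one of three levels, each with a grade: "Mild (equivalent to Grade 1) events are usually transient", "Moderate (equivalent to Grade 2) events introduce a low level of inconvenience" and "Severe (equivalent to Grade 3) events interrupt the". The list ends there.
- **Fallback scale, Protocol 9.4.** The rule begins "For AEs not covered by NCI CTCAE, the severity will be characterized as" and offers the same three levels. The top one opens "Severe events interrupt the". It attaches no grade numbers and has no level above severe.
- **Tabulation, SAP 10.2 (AE Summaries).** Subjects with adverse events are tabulated by relationship and by "severity (Grade 1 to Grade 5". A subject counts once per preferred term or system organ class, at the highest severity reported. SAP Section 14 lists an adverse-events-by-severity table for each part (14.3.1.9 in Part I, 14.3.1.8 in Part II).
- **Separate displays, SAP 10.3.** Serious adverse events and deaths get their own listings and summaries.
- **One explicit Grade 5 rule, Protocol 9.2.** Fatal progression of the malignancy under study is reported as Grade 5. The SAP does not repeat this rule, and no other event outside CTCAE has one.

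**The concern.** The conversion exists so that events outside CTCAE can sit in the same Grade 1 to 5 tables as the rest. It stops two levels short of the scale it feeds. A programmer who follows SAP 10.2 literally has no category above severe and must enter a fatal or life-threatening uncovered event as Grade 3.

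SAP 2.3.1 and Protocol 3.5.1 make the evaluation of treatment-related adverse events a primary endpoint, and the severity tables are one of its displays. Any misgrading runs in one direction, towards understating severity in a first-in-human trial. It would also leave the report inconsistent: the same event could be a death in the SAP 10.3 display and a Grade 3 event in the severity table.

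**Working it through.** The plan gives no figure to reproduce, so the check sets the rules side by side.

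**Step 1. What the rule returns.** SAP 10.2 orders Grades 1 to 5 by increasing severity and fixes severe at Grade 3. Protocol 9.2 pairs a fatal outcome with Grade 5 in the one case it covers. I take fatal as Grade 5 generally, and life-threatening as Grade 4 because it lies between severe and fatal. That reading is mine; the documents do not state it.

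| Event outside CTCAE | Highest level SAP 10.2 allows | Grade tabulated | Matching grade on the 1–5 scale | Understated by |
|---|---|---|---|---|
| Mild | Mild | 1 | 1 | 0 |
| Moderate | Moderate | 2 | 2 | 0 |
| Severe | Severe | 3 | 3 | 0 |
| Life-threatening | Severe | 3 | 4 | 4 − 3 = 1 grade |
| Fatal | Severe | 3 | 5 | 5 − 3 = 2 grades |

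**Step 2. Whether other text repairs it.** Protocol 9.4 does not, since it has the same three levels and no grades. Protocol 9.2 does so only for fatal progression of the cancer under study. SAP 10.3 shows the event elsewhere but does not change its grade in the severity table.

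**Step 3. When the error shows in a subject count.** Each subject counts at the worst grade within a term or organ class. The table is wrong for that subject only where no other event in the same row has a grade at least as high as the one lost. The effect on counts is therefore at most the number of subjects with an affected event, and can be smaller.

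**Step 4. Whether the right grade can be derived.** Protocol 9.3 requires seriousness and outcome to be recorded for every adverse event, and Protocol 9.8 lists outcome among the SAE form items. That supports deriving Grade 5. Protocol 9.2 names life-threatening as an SAE criterion, but the form items in Protocol 9.8 do not include which criterion was met. Grade 4 is derivable only if the eCRF holds that item, which the documents do not establish.

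**The case against.** The strongest reply is that this is a gap in a rarely used fallback. Deaths and serious events are reported separately, and Protocol 10.3.9 adds narratives for serious events. The severity tables are descriptive, and SAP 6.5 plans no inferential testing. No document gives an example of a serious event outside CTCAE. All of this stands and limits the importance of the point. It does not make the severity table right for an event that does fall under the rule.

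A reader might go further and infer that dose-limiting toxicities are lost. A hematologic event held at Grade 3 cannot meet the criterion "Grade 4 hematologic toxicity for > 1 day", so a cohort that should stop might seem to escalate. The documents do not support that:

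- The Grade 3 equivalence is only in the SAP. Escalation follows the protocol, with investigators consulted before each step (Protocol 3.1.2), a safety review before each new dose level (3.3), and committee review of every serious event (3.2).
- Non-hematologic DLTs already start at Grade 3, apart from the listed exceptions, so the cap removes none of them.
- For hematologic events, other DLT criteria remain: Grade 3 with complications, an interruption of more than 5 days in Cycle 1, or a delay of more than 7 days in starting Cycle 2. A patient who dies of a related toxicity in Cycle 1 cannot start Cycle 2, and Protocol 7.1 suspends the study for a related death.
- SAP Section 15 says the Part 1 plan was finalized earlier and that this version updates it for later amendments and the Part 2 displays.

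What remains is a logical corner case: a life-threatening hematologic event outside CTCAE, with no complication and no long interruption or delay. Nothing shows that it arises or that a dose decision would use the SAP mapping.

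A reader might also extend the point to the graded bar graphs. SAP 10.2 defines each bar by CTCAE term, so under that text an event outside CTCAE has no bar. Some Part II figure titles in Section 14 refer to preferred terms instead, which is a separate inconsistency.

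**Conclusion.** The point holds for the severity tabulations. SAP 10.2 states a conversion that cannot return Grade 4 or 5 and feeds it into tables that have those grades. The size is one grade for each life-threatening event and two for each fatal one, given the grade matching in Step 1.

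The number of such events is not in the documents and is probably small, so I give no percentage for the understatement of Grade 4 and 5 incidence. Any percentage would rest on a guessed count. No effect on DLT counts, the MTD, the RP2D or escalation decisions is shown. This is an inexpensive correction to one display of a primary safety endpoint.

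**What to change.** In SAP 10.2, add two levels to the conversion used for the severity tables:

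- **Fatal, equivalent to Grade 5.** Derive it from the adverse event outcome already recorded.
- **Life-threatening, equivalent to Grade 4.** Derive it from the SAE seriousness criterion, after the sponsor confirms that the eCRF captures that criterion and not only a yes/no seriousness flag.

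Add the same two levels to Protocol 9.4 so that the documents agree, and carry the Grade 5 rule for fatal progression from Protocol 9.2 into the SAP.

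The cost is a few lines of text and one extra derivation. No new data are needed for Grade 5. For Grade 4, that depends on the sponsor's confirmation.

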### Gastrointestinal Effects

Preclinical toxicity studies of BVD 523 have provided evidence of exposure-related, reversible gastrointestinal toxicities, and nausea, vomiting and diarrhea have been observed at high frequency in both BVD-523-01 and BVD-523-02, in some cases occurring in association with dehydration and elevated creatinine/renal insufficiency. Nausea, vomiting and diarrhea have been managed with BVD-523 dosing interruptions and supportive medications as needed and, in some cases, dose reduction of BVD-523 has been undertaken. Gastrointestinal hemorrhage (both upper and lower) has been reported in the BVD-523 program with the majority of events assessed as unrelated to study agent.

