14 TABLE OF CONTENTS FOR DATA DISPLAYS

TFL Shells are included as stand-alone documents.

Tables/Figures

Part I

Part I: Study Population

Part I - Table 14.1.1.1	Subject Disposition	ITT Population
Part I - Table 14.1.1.2	Analysis Population	ITT Population
Part I - Table 14.1.2	Protocol Deviations	ITT Population
Part I - Table 14.1.3.1	Demographic and Baseline Characteristics	Safety Population
Part I - Table 14.1.3.2	Demographic and Baseline Characteristics	ITT Population
Part I - Table 14.1.4.1	Prior Medications	Safety Population
Part I - Table 14.1.4.2	Concomitant Medications	Safety Population
Part I - Table 14.1.4.3	Concomitant Medication Taken for Adverse Events	Safety Population
Part I - Table 14.1.5.1	Treatment Compliance	Safety Population
Part I - Table 14.1.5.2	Exposure to Study Drug	Safety Population
Part I - Table 14.1.6	Pregnancy Test Results	Safety Population

Part I: Efficacy

Part I - Table 14.2.1	Target Lesion Response per RECIST 1.1	PP Population
Part I - Table 14.2.2	Non-Target Lesion Response per RECIST 1.1	PP Population
Part I - Table 14.2.3	New Lesion	PP Population
Part I - Table 14.2.4	Overall Response per RECIST 1.1	PP Population
Part I - Table 14.2.5	Best Overall Response per RECIST 1.1	PP Population
Part I - Table 14.2.6	Best Overall Response by Disease and Mutation Status	PP Population
Part I - Table 14.2.7	Duration of Best Overall Response by Disease and Mutation Status	PP Population

Part I: Safety

Part I - Table 14.3.1.1	Dose Limiting Toxicities	Safety Population
Part I - Table 14.3.1.2	Details of Dose Limiting Toxicities	Safety Population
Part I - Table 14.3.1.3	Doses Selected as MTD and RP2D	Safety Population
Part I - Table 14.3.1.4.1	Frequency and Reasons for Dose Delays/Interruptions	Safety Population
Part I - Table 14.3.1.4.2	Duration of Dose Delays/Interruptions	Safety Population
Part I - Table 14.3.1.5	Adverse Events	Safety Population
Part I - Figure 14.3.1.5	Bar Graph of Adverse Events	Safety Population
Part I - Table 14.3.1.6	Serious Adverse Events	Safety Population
Part I - Figure 14.3.1.6	Bar Graph of Serious Adverse Events	Safety Population
Part I - Table 14.3.1.7	Adverse Events Leading to Premature Discontinuation from the Study	Safety Population
Part I - Figure 14.3.1.7	Bar Graph of Adverse Events Leading to Premature Discontinuation from the Study	Safety Population
Part I - Table 14.3.1.8	Adverse Events by Relationship to Study Drug	Safety Population

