Part I - Table 14.3.1.9	Adverse Events by Severity	Safety Population
Part I - Table 14.3.2.1	Treatment Emergent Adverse Events	Safety Population
Part I - Figure 14.3.2.1	Bar Graph of Treatment Emergent Adverse Events	Safety Population
Part I - Table 14.3.2.2	Serious Treatment Emergent Adverse Events	Safety Population

Part I: Death Narratives

Part I: Laboratory Results

Part I - Table 14.3.4.1	Laboratory Evaluations – Hematology	Safety Population
Part I - Table 14.3.4.2	Laboratory Evaluations – Clinical Chemistry	Safety Population
Part I - Table 14.3.4.3	Laboratory Evaluations – Urinalysis	Safety Population

Part I: Physical Examination Results

Part I - Table 14.3.5.1	Physical Examinations	Safety Population
Part I - Table 14.3.5.2	ECOG Performance Status	Safety Population
Part I - Table 14.3.5.3	Electrocardiograms	Safety Population
Part I - Table 14.3.5.4	Categorized Electrocardiograms	Safety Population
Part I - Table 14.3.5.5	Ophthalmology Examinations	Safety Population
Part I - Table 14.3.5.6	Vital Signs	Safety Population

Part I: Pharmacokinetics

Part I - Table 14.4.1	Pharmacokinetic Parameters Calculated from Blood Samples	PK Population
Part I - Table 14.4.2	Pharmacokinetic Parameters Calculated from Urine Samples	PK Population

Part I: Pharmacodynamics

Part I - Table 14.5.1	Fluid Pharmacodynamics	Pharmacokinetics Population
-----------------------	------------------------	-----------------------------

Part I: Tumor Genotyping

Part I - Table 14.6.1	Tumor Genetic Information	PP Population
-----------------------	---------------------------	---------------

Part II

Part II: Study Population

Part II - Table 14.1.1.1	Subject Disposition	mITT Population
Part II - Table 14.1.1.2	Analysis Population	mITT Population
Part II - Table 14.1.2	Protocol Deviations	mITT Population
Part II - Table 14.1.3.1	Demographic and Baseline Characteristics	Safety Population
Part II - Table 14.1.3.2	Demographic and Baseline Characteristics	mITT Population
Part II - Table 14.1.4.1	Prior Medications	Safety Population
Part II - Table 14.1.4.2	Concomitant Medications	Safety Population

Part II - Table 14.1.4.3	Concomitant Medication Taken for Adverse Events	Safety Population
Part II - Table 14.1.5.1	Treatment Compliance	Safety Population
Part II - Table 14.1.5.2	Exposure to Study Drug	Safety Population
Part II - Table 14.1.6	Pregnancy Test Results	Safety Population
Part II: Efficacy		
Part II - Table 14.2.1	Target Lesion Response per RECIST 1.1	PP Population

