Part II - Figure 14.2.1	Genetic Information Leading to Target Lesion Response	PP Population
Part II - Table 14.2.2	Non-Target Lesion Response per RECIST 1.1	PP Population
Part II - Table 14.2.3	New Lesion	PP Population
Part II - Table 14.2.4	Overall Response per RECIST 1.1	PP Population
Part II - Table 14.2.5	Best Overall Response per RECIST 1.1	PP Population
Part II - Figure 14.2.6	Genetic Information Leading to Best Overall Response	PP Population
Part II - Table 14.2.7	Best Overall Response by Disease and Mutation Status	PP Population
Part II - Table 14.2.8	Duration of Best Overall Response by Disease and Mutation Status	PP Population
Part II: Safety		
Part II - Table 14.3.1.1	Dose Limiting Toxicities	Safety Population
Part II - Table 14.3.1.2	Details of Dose Limiting Toxicities	Safety Population
Part II - Table 14.3.1.3	Duration of Dose Interruptions	Safety Population
Part II - Table 14.3.1.3	Adverse Events	Safety Population
Part II - Figure 14.3.1.4.1	Bar Graph of Adverse Events by PT	Safety Population
Part II - Figure 14.3.1.4.2	Bar Graph of Adverse Events by SOC and PT	Safety Population
Part II - Table 14.3.1.5	Serious Adverse Events	Safety Population
Part II - Figure 14.3.1.5.1	Bar Graph of Serious Adverse Events by PT	Safety Population
Part II - Figure 14.3.1.5.2	Bar Graph of Serious Adverse Events by SOC and PT	Safety Population
Part II - Table 14.3.1.6	Adverse Events Leading to Premature Discontinuation from the Study	Safety Population
Part II - Figure 14.3.1.6.1	Bar Graph of Adverse Events Leading to Premature Discontinuation from the Study by PT	Safety Population
Part II - Figure 14.3.1.6.2	Bar Graph of Adverse Events Leading to Premature Discontinuation from the Study by SOC and PT	Safety Population
Part II - Table 14.3.1.7	Adverse Events by Relationship to Study Drug	Safety Population
Part II - Figure 14.3.1.8.1-1	Bar Graph of Probably Related Adverse Events by PT	Safety Population
Part II - Figure 14.3.1.8.1-2	Bar Graph of Possibly Related Adverse Events by PT	Safety Population
Part II - Figure 14.3.1.8.1-3	Bar Graph of Unrelated Adverse Events by PT	Safety Population
Part II - Figure 14.3.1.8.2-1	Bar Graph of Probably Related Serious Adverse Events by PT	Safety Population
Part II - Figure 14.3.1.8.2-2	Bar Graph of Possibly Related Serious Adverse Events by PT	Safety Population
Part II - Figure 14.3.1.8.2-3	Bar Graph of Unrelated Serious Adverse Events by PT	Safety Population

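### The AE counting rule takes the highest grade and the greatest relationship separately, so the Part II bar graphs split by relationship can show a related high-grade AE that did not occur

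*SAP*

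**What the plan says.** SAP 10.2, under AE Summaries, sets the counting unit: "A subject who reported multiple AEs that map to a common PT or SOC is counted only once for that PT or SOC". That single count is placed "at the highest severity reported and at the greatest relationship to study drug". Relationship has three levels in SAP 10.2: unrelated, possibly related and related.

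The same section then describes a tabulation "with respect to relationship to study drug (unrelated, possibly related, and related) and severity (Grade 1 to Grade 5", without saying whether the two attributes are crossed or tabulated one at a time. For the bar graphs it adds: "Severity of AE (grades) will be embedded in each bar using the percentages of patients in each AE grade". It says that such plots accompany every AE table.

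The display list in SAP 14 has one table titled "Adverse Events by Relationship to Study Drug" and another titled "Adverse Events by Severity" in each study part (Part I Tables 14.3.1.8 and 14.3.1.9; Part II Tables 14.3.1.7 and 14.3.1.8). It lists no table of relationship by severity. For Part II it also lists six bar graphs split by relationship, three for AEs and three for SAEs, for example "Bar Graph of Possibly Related Adverse Events by PT". All six are by preferred term.

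The evaluation of treatment-related AEs is one of the four primary safety endpoints (Protocol 3.5.1, SAP 2.3.1).

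**The concern.** Two maxima taken over the same set of events need not belong to the same event. While each is reported in its own table, this does no harm. Once relationship and grade appear in one display, the pair can describe something that happened to nobody.

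A bar graph limited to one relationship category, with each bar divided by grade, is such a display. Among the listed AE summaries, the six Part II figures are where relationship and grade visibly meet. A reader who wants to know how severe the drug-related events were will therefore turn to them. At stake is the grade profile of related AEs, which bears on a primary endpoint, and the completeness of the figures for the lower relationship categories.

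**Working it through.** The plan states no figure for this rule, so there is nothing to reproduce. The check applies the rule to two constructed subjects, each with two events under one preferred term.

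| | Subject A | Subject B |
|---|---|---|
| Event 1 | Grade 3, unrelated | Grade 3, possibly related |
| Event 2 | Grade 1, related | Grade 1, related |
| Highest grade | 3 | 3 |
| Greatest relationship | related | related |
| Pair under the SAP rule | Grade 3, related | Grade 3, related |
| Is the pair a real event? | no | no |

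**Separate tables.** The severity table shows Grade 3 and the relationship table shows related. Both entries are true for both subjects.

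**Figures split by relationship, with grades in the bars.** In the figure for the top category, each subject is placed in the Grade 3 segment, although the only related event was Grade 1. Because a subject counts once, at the greatest relationship, A's Grade 3 event is missing from the unrelated figure and B's from the possibly related figure.

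**Restricting by category first, then taking the highest grade.** Subject A appears as Grade 1 in the related figure and Grade 3 in the unrelated figure. Subject B appears as Grade 1 in the related figure and Grade 3 in the possibly related figure. Every entry is a real event. If possibly related and related are pooled, A is Grade 1 and B is Grade 3, again both real.

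**Direction.** The highest grade over all events is at least the highest grade over the related ones. The rule can therefore overstate the grade of related AEs but never understate it. The total height of a bar in the top category is right, since it counts subjects with at least one related event; only its division by grade can be wrong. The lower-category figures can lose subjects.

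**Size.** The share of subjects affected is the probability of having, under one term, a high-grade event in a lower category together with a low-grade related event. The documents give no rate for that combination. The effect of one such subject is:

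- Group of 15 (the cap on evaluable patients per group, Protocol 3.1.2): 1/15 = 0.067, or 6.7 percentage points moved from the Grade 1 to the Grade 3 segment.
- All Part 2 patients pooled (about 105, Protocol 4.1): 1/105 = 0.0095, or about 1 point.

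The figure titles do not say whether the graphs are drawn by group or pooled. The denominator is the Safety Population, so it can differ from 15 if a group does not fill or if withdrawn patients are replaced.

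**The case against.** The strongest reply is that SAP 10.2 does not give the order of operations for the figures. A programmer could select events by relationship first and then take the highest grade, which would remove the problem. The table and figure shells that might settle this are stand-alone documents and are not part of the material. This stands in part: the error depends on how the figures are programmed. But selecting first lets one subject appear in two relationship figures for the same term, which the stated once-only count at the greatest relationship does not allow. Read literally, the written rule leads to the error.

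Three further replies stand in full:

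- The listed tables by relationship and by severity are separate, and this is a natural reading of the tabulation sentence in SAP 10.2. A cross-table is possible under that sentence but is not in the display list.
- DLTs are defined from drug-related toxicities meeting stated criteria, and the MTD from DLTs. The RP2D is settled in discussion that may draw on PK, pharmacodynamic and cumulative toxicity observations. None of these is defined through the collapsed summary.
- Event-level AE listings are planned, so the true pairs can be recovered, and no inferential testing is planned.

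A reader might also infer a larger effect at system organ class level. Nausea and diarrhea are frequent, and the Protocol describes gastrointestinal hemorrhage "with the majority of events assessed as unrelated to study agent", so one might expect many false related high-grade entries for the gastrointestinal class. The documents do not support this. The relationship-split figures are by preferred term, so nausea and hemorrhage never share a bar, and the figures listed by system organ class are not split by relationship. That reading needs a class-level cross-table which the display list does not contain. The rates needed to size it are not given either.

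**Conclusion.** The point holds for displays that combine relationship and grade: the six Part II relationship figures, and a cross-table if SAP 10.2 means one. There, a subject with a high-grade event in a lower relationship category and a low-grade related event under the same term is shown with a related high-grade AE that did not occur, and is lost from the lower-category figure.

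This rests on two assumptions: that the rule is applied as written before the events are split by relationship, and that some subjects have the same term more than once with different attributions. The second is plausible, since treatment continues over repeated cycles and AEs are collected until 30 days after the last dose, but its frequency cannot be derived from the documents. Each such subject moves 6.7 points in a group of 15.

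It would go too far to say that the primary endpoint as a whole is distorted. The separate tables are correct, and the DLT, MTD and RP2D determinations are untouched. The issue is a stated rule that misdescribes the grade of related AEs in a small set of figures.

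**What to change.** Revise the AE Summaries text in SAP 10.2 to state that:

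1. For the separate tables, severity and relationship are each collapsed to the subject's maximum, independently.
2. For any display by relationship and grade, events are first restricted to that relationship category (or to possibly related and related pooled), and the subject's highest grade is then taken among those events only.
3. As an exception to the once-only count, a subject may appear in more than one relationship display for the same term.

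Say also whether the tabulation by relationship and severity is two tables or a cross-table. Align the SAP 14 figure titles with the three relationship levels: some use Probably Related, which is not on the SAP's scale.

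The cost is a few sentences, a small program change and corrected titles. The one drawback is that counts across the relationship figures for a term may add up to more than the number of subjects with that term, so a footnote should say so.
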